#### **Intake and Consent Process:**

##### **For MUSC Charleston patients:**

If the electronic medical record identifies them as a smoker, or if they report being a smoker at the time of their scan, they will meet or speak by phone with one of our study research assistants. Patients who express interest in the study will set up an intake appointment with a research staff member within 60 days of the date of their shared decision making visit. Patients who decline to participate in the study will be asked why and will be asked if we can collect basic demographic data from their medical record (e.g., age, gender, race, ethnicity, pack years). All eligible lung cancer screening patients will receive a postcard prior to their appointment informing them that they may be eligible to participate in a research study. The study staff will call these patients prior to their appointment to gauge interest in the study. If the patient would like more information, a study staff member will either meet the patient at the scanner on their proposed scan date, at another agreed upon time and place, or speak by phone. If the patient is interested in enrolling or getting more information about the study, a research assistant will speak to them or set a date with the patient to enroll them into the study. Study eligibility will be determined in concert with a clinic staff member and the site PI ([name] at MUSC or [name] at Yale) following completion of baseline assessments, a review of the electronic medical record for health information (if necessary), and the eligibility checklist.

Informed consent will be obtained prior to any other procedures. We will provide participants with the option to complete consent and/or baseline session 1) in person, 2) via an MUSC approved HIPAA compliant video

**Commented [TB1]:** [name], would you please frame this to the IRB like this:

We chose to change our inclusion of potential participants from the day of the scan to the day of the shared decision making visit because although these 2 events generally occur on the same date, it is possible that patients may engage in a shared decision making visit and decline participation in the scan. We feel this is an important population to include in the study.

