If a patient, using the remote study visit option, is randomized into a group receiving NRT, the medications will be mailed to the participant as soon as possible. If a patient is randomized into the gain-framed group, they will be asked to view the gain-framed video via an emailed or texted link and the gain-framed materials will be mailed to them as soon as possible. Following the consent process, patients will also be asked to complete the baseline assessments during their first meeting. If they are unable to complete these during this appointment, research staff will remind them to complete these assessments within a week. Additionally, after consent has been obtained and eligibility has been established, we will offer participants the option to complete the baseline assessments at another time (including by phone) within a week of the start of the intake session to allow for greater flexibility to accommodate participant schedules. The study visit will be done at the clinic, at a public location convenient for the participant, or via phone. Participants will be paid \$50 for completion of all intake assessments.

For MUSC Lancaster, MUSC Chester, MUSC Florence, and MUSC Columbia patients:

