If an eligible patient from either MUSC Lancaster/Chester/Florence/Columbia is interested in enrolling into the study, all study procedures will take place remotely. It is not feasible to perform study procedures in person due to the far distance from study staff, who are located at MUSC Charleston. Recruitment and all study procedures will follow the same procedures as described above for MUSC Charleston sites, with the exception of using in-person methods. If the electronic medical record identified the patient as a smoker, or if the patient reports being a smoker at the time of their scan, the nurse practitioner will speak with the patient regarding the study and/or the patient will speak by phone with one of our study research assistants. The nurse practitioner will be given study flyers to hand out to eligible patients. Patients who express interest in the study will set up an intake appointment with a research staff member 60 days of the date of their shared decision making visit. Patients who decline to participate in the study will be asked why and will be asked if we can collect basic demographic data from their medical record (e.g., age, gender, race, ethnicity, pack years). All eligible lung cancer screening patients will receive a postcard prior to their appointment informing them that they may be eligible to participate in a research study. The study staff will call these patients to gauge interest in the study. If the patient would like more information, the study staff will meet with the patient virtually. All study visits from the MUSC Lancaster/Chester/Florence/Columbia sites will be conducted remotely. After the patient is

randomized into the study, they will be mailed study intake materials (i.e., wellness bag, written materials, and NRT if applicable). Study participants from this site will be paid using Amazon e-gift cards.

For patients at the VA:

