#### Standard Care for Smoking Cessation Advice for All Study Participants:

Upon consent, all participants will be randomized to study group, stratified by study site and level of motivation (low: 0-7 on VAS ladder vs. 8-10). Following randomization, all participants will receive a bag with small smoking cessation tools (i.e., stress ball) and smoking cessation handouts based on practical counseling principles, which is a cognitive-behavioral, evidence-based, smoking cessation treatment modality focused on specific strategies to support quitting smoking. If patients are meeting with research staff via tele-consent, e-consent, or by mail, the wellness bag will be mailed to them with the intervention materials they were randomized to receive. All participants will be encouraged to set a quit date.

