#### Study Interventions:

Gain-Framed Messaging: We will develop 1 gain-framed video and corresponding printed materials. The video will be approximately 4 minutes long and will include individuals of differing racial and ethnic backgrounds representative of our study population. The video will be designed specifically for lung screening patients, addressing how quitting smoking can be helpful given their present situation. To be clear, we are not framing any information to encourage lung screening – the gain-framed intervention will focus on smoking cessation in the context of lung screening. It will highlight [name] recent paper showing that quitting smoking will significantly reduce their risk for lung cancer in conjunction with screening. For example, a gain-framed statement in this regard might say: "Attending this lung screening visit and low-dose CT screen is a great step toward better health and reducing your risk of lung cancer. Even if you decide not to undergo screening, you can still further reduce your risk of developing lung cancer and other diseases by quitting smoking. Research of high risk people who did not have a CT scan shows that by quitting smoking and maintaining abstinence you continue to reduce your risk for lung cancer."

For those in the arm that will receive gain-framed materials, we will disseminate the gain-framed print media to patients at the time of intake. A research assistant will show participants their assigned video via an iPad if they are assigned to the GM+M groups. We chose these procedures for several reasons: a) delivering the gain-framed messages by video allows us keep the content consistent, b) videos are easily disseminable, c) having our research staff administer the videos is consistent with how the videos would be administered at other lung screening programs (i.e., given by support staff and not clinicians), and d) this does not necessitate any special training or procedures with the clinical staff.

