#### **PROTECTION OF HUMAN SUBJECTS**

##### **RISKS TO THE SUBJECTS**

##### **Human Subjects Involvement and Characteristics**

In this experiment, participants will be recruited to participate in a smoking cessation study in the context of lung cancer screening. For the randomized controlled study, we will use the following inclusion and exclusion criteria. Inclusion: 1) 50 years or older (we see no reason for upper limit given supportive evidence for cessation among elderly), 2) 20 pack year history of smoking (i.e., the base population of high risk smokers to get screened), 3) current smoker (defined as any smoking in the past 30 days – this is the criteria our lung cancer screening programs will use to trigger tobacco treatment interventions), 4) willing to be randomized, 5) English speaking; Exclusion: 1) unstable psychiatric/medical conditions such as suicidal ideation, acute psychosis, severe alcohol dependence, or dementia, and 2) contraindications to NRT. We intend to enroll 616 participants across 3 sites (MUSC, VA and Yale).

**Sources of Materials.** The sources of data for participants in this project is open-ended questions through interviewer-administered self-report questionnaires of background, behavior (eg, smoking), and cognitions (eg, motivation). Questionnaires will be administered at the time of intake (i.e., the lung cancer screening appointment), and at 1, 3, and 6 months for follow-up. All responses will be collected on a secure, password-

protected, electronic Web-based form. The data will be sent to a secure database in REDCap. Only research staff members have access to the database. The data obtained from VA participants will be housed in the VA REDCap database.

We will collect demographic information, as well as diagnostic medical information related to their screening. Identifiable information will be collected and used to enroll, treat, and contact participants. It will only be used for this purpose.

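### The MUSC intake text lets baseline scales be deferred for up to a week and does not hold randomisation or delivery until they are complete, so some mediator and FTND/HSI baselines may follow allocation (minor)

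*Combined protocol and SAP*

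**What the plan says.** Under Intake and Consent Process, For MUSC Charleston patients, eligibility is determined "following completion of baseline assessments", together with a records check where needed and the eligibility checklist.

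The same section then opens two routes to a later baseline:
- For participants who do not finish at the first meeting: "If they are unable to complete these during this appointment, research staff will remind them to complete these assessments within a week".
- As a planned option: "after consent has been obtained and eligibility has been established, we will offer participants the option to complete the baseline assessments at another time". The limit is one week from the start of the intake session, and completion by phone is allowed.

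The section for the Lancaster, Chester, Florence and Columbia locations carries this over, apart from in-person methods: "Recruitment and all study procedures will follow the same procedures as described above for MUSC Charleston sites".

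On allocation, the Standard Care section says: "Upon consent, all participants will be randomized to study group, stratified by study site and level of motivation".

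Delivery follows quickly. Study Interventions states that "we will disseminate the gain-framed print media to patients at the time of intake", and that research staff show the video on a tablet. Under NRT sampling, participants may try a patch and a lozenge at the study visit. For remote participants in the gain-framed arm, "they will be asked to view the gain-framed video via an emailed or texted link", and the print materials and NRT are mailed promptly.

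The Statistical Analysis section hypothesises mediation through changes in self-efficacy, outcome expectancies and familiarity with NRT, among others. It requires a moderator to exist before randomisation and to be unrelated to treatment. The Assessments section names FTND and HSI as moderators.

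**The concern.** A change score needs a starting value taken before the intervention can act. If a participant has already watched the video, read the print material or used NRT when the baseline scale is completed, part of the effect is already in the baseline, and the measured change tends to be too small.

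The moderator analysis is exposed in a different way. HSI is scored from amount smoked and time to first cigarette, and early NRT use or a quit attempt can alter both. Only the GM+M arm receives the video and the NRT, so a late score can differ between arms because of treatment. That is what the plan's moderator rule is meant to exclude.

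There is a third route. Statistical Analysis takes baseline characteristics associated with smoking outcomes into model development, and runs the primary and secondary models both unadjusted and adjusted. A late FTND or HSI score could then enter an adjusted efficacy model as a post-randomisation covariate.

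**Working it through.** The point turns on sequence, so the check sets the statements side by side. There is no plan figure to reproduce.

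| Step | Where stated | Order implied |
|---|---|---|
| Eligibility | MUSC Charleston intake | After baseline is complete |
| Deferred baseline | MUSC Charleston intake | After consent and eligibility, up to one week from the start of intake |
| Randomisation | Standard Care section | At consent, stratified by site and motivation |
| Video and print | MUSC Charleston intake; Study Interventions | At intake, or by link and prompt mailing |
| NRT | MUSC Charleston intake; NRT sampling | At the study visit, or by prompt mailing |

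1. **Is there a contradiction?** Yes. If eligibility needs a completed baseline, the baseline cannot be offered for completion after eligibility is established. Both sentences cannot be followed for the same participant.

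2. **Can a deferred baseline come after allocation?** The Standard Care sentence cannot mean the instant of consent, because stratification needs the motivation ladder first. The ladder is, however, the only baseline score it makes a condition of randomisation. No other section adds the remaining scales as a condition, or holds back delivery. For someone who defers, the sequence consent, eligibility, ladder, randomisation, exposure, remaining scales is consistent with the text.

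3. **Which measures are exposed?**
   - Not the motivation ladder, which is needed for stratification.
   - Possibly not confidence or smoking history. Confidence is assessed alongside motivation, and the baseline history is used to personalise the gain-framed messages. Self-efficacy is a single confidence item and could be collected with them.
   - Outcome expectancies (six items), NRT attitudes and knowledge, and FTND/HSI have no stated reason to come before randomisation, although the two HSI items could be taken with the smoking history.

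4. **Which participants?** MUSC participants who defer or do not finish. The mail route sends the questionnaire with the consent form, so it is not counted. The VA section does not restate the deferral, so the VA is not counted either.

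5. **Direction of the effect on mediators.** Let D be the true arm difference in change, f the share of the GM+M arm whose baseline follows exposure, and r the fraction of the effect already present by then. If the control baselines are unmoved, the observed difference is D × (1 − f × r), which is smaller than D whenever f and r are both above zero. The documents give neither f nor r, so no figure is put on the loss.

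**The case against.** The strongest reply is that a late baseline is an inference. No section says that deferred assessments follow randomisation. The default path reads naturally as consent, baseline, eligibility, randomisation and delivery, and both stratification and message personalisation presuppose some assessment first. This stands, and it limits the point to the deferral routes and to what the text permits. A reader might infer that baselines were in fact taken after exposure, or that the whole battery was. The documents support neither.

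A second reply is that the moderator rule in Statistical Analysis already screens out a late FTND or HSI score. In principle it does. It can be applied only if the dates of baseline and randomisation are recorded and compared, and it does nothing for the change-score mediators.

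A third concerns the Sources of Materials paragraph: "Questionnaires will be administered at the time of intake (i.e., the lung cancer screening appointment"). A reader might count this as another contradiction. It is a general description of data sources and can be read together with a window that runs from the start of intake, so no weight is placed on it.

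A reader might also extend the point to scan findings that are reported after randomisation. The moderator rule asks that the variable be present, not that its result be known, and nothing in the documents suggests that the interventions would cause a nodule or emphysema. Excluding such findings could discard valid data.

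**Conclusion.** The point holds as a minor one. The order of baseline and eligibility is contradictory in the current text, and the deferral option permits some MUSC baseline scales to be completed after allocation and exposure.

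The affected analyses are the exploratory mediator and moderator analyses and, through covariate selection, possibly the adjusted primary and secondary models. It would be wrong to infer that the main result is at risk: the unadjusted intention-to-treat comparison of abstinence uses none of these scales.

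The size is unknown. It depends on how many participants defer, how soon the materials reach them, and how quickly the scales respond, and the documents give none of these for this trial. The expected direction for the mediators is understatement, on the assumption that exposure moves the scale towards its later value and leaves the control baselines alone.

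Some of the information survives. Follow-up mediator levels can be compared between arms without a baseline. The calendar covering the 30 days before treatment gives a check on amount smoked, though not on time to first cigarette.

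**What to change.** Reconcile the MUSC intake text with the Standard Care section so that one order applies: consent; then the motivation ladder, self-efficacy, outcome expectancies, NRT attitudes and knowledge, and FTND/HSI; then randomisation; then delivery of the video, print and NRT. Keep the one-week window for the other questionnaires. Record the dates of baseline completion, randomisation and first exposure to each intervention component.

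For participants already enrolled:
- Report the number of late baseline values by arm.
- Leave late FTND/HSI scores out as moderators and as adjustment covariates in the main version of those analyses.
- Run the mediator analyses with and without late baselines.
- As supporting checks, compare follow-up mediator levels between arms and compare the HSI amount item with the pre-treatment calendar.

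The cost is a short amendment and a few date fields. Some intakes will be longer or have to be rescheduled; how many depends on the unknown share who would otherwise defer.

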#### Medication Dispersal for patients at the VA:

The research assistant will let the research pharmacist and [name] know in advanced when they will be at the VA to screen potential research participants. [name] will electronically enter the order for the two-week supply of Nicotine patches and mini lozenges before randomization because she is not always available to enter medication orders at the time of intake. After a patient has been screened and has signed the Informed Consent, the ICF will be sent to the research pharmacist via the VA email or taken to the research pharmacy in person and copy is made. The research assistant will contact the research pharmacist via phone or Vocera to inform them of the randomization. The research pharmacist will fill the order that will then be picked up by the research assistant and given to the patient in person. If the patient is using the remote consent option, the medications will be mailed to the patient after randomization is confirmed by the research pharmacy. If the patient is unable to complete the intake appointment the same day as their lung cancer screening visit, the research assistant will let research pharmacist know when the appointment is scheduled for. [name] will put the order in for the NRT within a week of the patient's appointment. If the patient is randomized into a group NOT receiving NRT the order will be cancelled.

#### Standard Care for Smoking Cessation Advice for All Study Participants:

Upon consent, all participants will be randomized to study group, stratified by study site and level of motivation (low: 0-7 on VAS ladder vs. 8-10). Following randomization, all participants will receive a bag with small smoking cessation tools (i.e., stress ball) and smoking cessation handouts based on practical counseling principles, which is a cognitive-behavioral, evidence-based, smoking cessation treatment modality focused on specific strategies to support quitting smoking. If patients are meeting with research staff via tele-consent, e-consent, or by mail, the wellness bag will be mailed to them with the intervention materials they were randomized to receive. All participants will be encouraged to set a quit date.

#### Study Interventions:

Gain-Framed Messaging: We will develop 1 gain-framed video and corresponding printed materials. The video will be approximately 4 minutes long and will include individuals of differing racial and ethnic backgrounds representative of our study population. The video will be designed specifically for lung screening patients, addressing how quitting smoking can be helpful given their present situation. To be clear, we are not framing any information to encourage lung screening – the gain-framed intervention will focus on smoking cessation in the context of lung screening. It will highlight [name] recent paper showing that quitting smoking will significantly reduce their risk for lung cancer in conjunction with screening. For example, a gain-framed statement in this regard might say: "Attending this lung screening visit and low-dose CT screen is a great step toward better health and reducing your risk of lung cancer. Even if you decide not to undergo screening, you can still further reduce your risk of developing lung cancer and other diseases by quitting smoking. Research of high risk people who did not have a CT scan shows that by quitting smoking and maintaining abstinence you continue to reduce your risk for lung cancer."

For those in the arm that will receive gain-framed materials, we will disseminate the gain-framed print media to patients at the time of intake. A research assistant will show participants their assigned video via an iPad if they are assigned to the GM+M groups. We chose these procedures for several reasons: a) delivering the gain-framed messages by video allows us keep the content consistent, b) videos are easily disseminable, c) having our research staff administer the videos is consistent with how the videos would be administered at other lung screening programs (i.e., given by support staff and not clinicians), and d) this does not necessitate any special training or procedures with the clinical staff.

The most appropriate comparison group for the gain-framed intervention is debatable; we could have used a loss-framed or general health video/print intervention as a comparator but we decided against this for several reasons: a) it is more translational and more of a "real-world" test to only investigate an intervention that we hypothesize may be better than standard care; b) we do not want to waste participants' time with placebo video and handouts that we expect will not help them; and c) notably, our last large smoking cessation trial that

tested message framing was a comparison of standard care to a gain-framed intervention added to standard care, for similar reasons to those described above. Thus, our control condition for the gain-framed message conditions is no message.

**NRT sampling:** Participants in the medication arm (GM+M) will be given a 2-week long supply of both nicotine patch and lozenge. NRT samples will be delivered in addition to all standard care treatment described above. Given the very brief 'intervention' time (few minutes), we believe that treatment groups will be essentially time-matched. We will provide a 2-week supply of both 4 mg lozenge and 21mg nicotine patches provided in the original packaging. Detailed information on each product, including instructions for use, will be provided in the take-home packet, which will include FAQs and related information intended to dispel medication misperceptions. Patients who are receiving nicotine patches and lozenges will be given the option to try these over-the-counter products (i.e., a patch and a lozenge) at the time of their study visit with aid from the research staff and will receive handouts and instructions about proper use of the NRT. We provide both patch and lozenge for four reasons. **First**, a number of studies demonstrate their efficacy when used singularly. **Second**, they are both over the counter, increasing their utility in various populations, particularly within lung cancer screening settings where eligibility is minimal and instructions on use require nominal discussion. **Third**, whereas the patch provides a steady dose of nicotine throughout the day, the lozenge is used ad libitum and provides acute nicotine administration. These two mechanisms might appeal to smokers differently. **Fourth**, two studies have shown that combined use of patch + lozenge is superior over placebo and single NRT products. We neither explicitly advise nor discourage combined use. Thus, this is an opportunity for smokers to learn about two NRT products, to be used individually or together (participant choice, including none at all). We will caution all participants on signs of receiving too much nicotine (nausea, dizziness), and will monitor adverse events, expected to be rare/mild. Given our inclusive study criteria, some study participants who have low nicotine dependence will receive the starter package of NRT. However, given recent evidence that dual NRT benefits most low dependence smokers, we feel this is appropriate. We do not offer a placebo comparison because we are interested in the provision of medication vs. not (and not to determine if effects are pharmacologic). However, participants not receiving the starter kit of NRT will still be advised to use evidence based medications, including NRT, per standard guidelines. The NRT for MUSC patients will be stored in a cabinet in the Tobacco Treatment Program offices. The door to the office suite locks. The NRT for VA patients will be obtained via the research pharmacy at the Ralph H Johnson VA Medical Center.

**Follow-up:** Participants will complete assessments at a 1, 3, and 6 month follow-up session. Research staff will meet the MUSC Charleston participant in a public location that is convenient to the participant or conduct the follow-up via phone call. MUSC Charleston patients will also have the option of coming in to the clinic at Hollings Cancer Center for the follow-up meeting. All participants recruited from MUSC Lancaster, MUSC Chester, MUSC Florence, and MUSC Columbia will complete all visits remotely. If the participant has an in-person meeting, we will complete a breath CO test and a battery of assessments. If patients elect to complete these visits via phone call and report that they continued to smoke, a CO breath test will not be obtained. However, if the patient reports having quit smoking during the phone call, the research staff will schedule a visit to obtain the CO breath test. CO will be collected using the Bedfont Smokerlyzer for in-person visits or the Bedfont iCO smokerlyzer for remote visits. If CO is obtained remotely, we will mail a breath CO monitor to the participants with instructions for use. At a prearranged time, participants will be sent a link to a HIPAA Compliant video platform. Participants will virtually meet with research staff and will complete the breath CO sample live so that we can be sure it was the participant who provided the sample and reduce the chance of sample falsification. The CO device will also email a report of the CO sample to research staff. We plan to pay participants \$10 for completion of the 1- and 3-month follow up visits and \$30 for the completion of the 6-month visit. If the study participant is not available to meet in person or by phone, we will mail the follow up questionnaire to them to fill out and return via mail to us. Additionally, we can also send patients a link to the questionnaires via REDCap and contact them over the phone to get their timeline followback.

**Safety protocol:** To ensure the safety of the research assistant they will adhere to the following safety guidelines:

- Confirm with participants by phone before the visit
- Send meeting information to the Study Coordinator prior to leaving for the meeting
- Meet in public buildings where you feel safe, and not in parking lots, or public parks

Send a message to the Study Coordinator to confirm that the meeting has ended and you are leaving the meeting location

Never meet a participant after dark

Keep your phone charged and on your person at all times in case of emergency

To ensure the safety and privacy of the MUSC participant:

We will try to meet in a public location that has an area that is in clear sight of others but semi-private area where we can obtain research data as confidentially as possible.

We will not use the patient's name in public at this location.

We will speak in low volume to communicate with the participant as not to share information with those in the surrounding area.

To ensure the safety and privacy of the VA participant:

We create a VA REDCap database behind the VA firewall where all participant study data will be collected, stored and analyzed.

Assessments (Items with an asterisk will be tested as a mediator or moderator):

Demographic and Smoking History Questionnaire: As in our previous studies, this questionnaire will obtain: 1) basic demographic information and 2) basic smoking status and history. At baseline this will assess basic smoking status and history which will allow us to personalize the messages for participants in the study groups receiving gain-framed messages.

Tobacco and Alcohol Use Calendar (Timeline Followback): This standardized, validated, and reliable experimenter-administered rating scale will be used to obtain quantity and frequency estimates of cigarette consumption for a 30-day period prior to treatment. As in our previous clinical trials, we will use the calendar to record tobacco use on a daily basis throughout the 6 months of the study.

Abstinence: For our primary outcome, consistent with our past clinical trials, abstinence will be defined as 7-day point prevalence abstinence, meaning no cigarettes (or other tobacco products) for 7 days, confirmed by CO breath test less than or equal to 10 ppm.

CO levels: Expired breath CO will be monitored at each in-person visit to verify abstinence during treatment. Levels of CO will be measured using a Bedfont Micro+ Smokerlyzer Monitor (Innovative Medical Marketing, Williamsburg, VA), which is a precision instrument for detecting CO in exhaled breath. Both study sites are currently using these devices and have several on hand. If smoking status is verified remotely, participants will be mailed a Bedfont iCO Smokerlyzer with instructions for use. They will complete the breath test live on a HIPAA compliant video platform and results will be emailed to study staff.

Evaluation of Framed Intervention: This manipulation check asks participants to report whether the session focused on the costs of continuing to smoke or the benefits of smoking cessation.

\*Outcome expectancies: Expectancies regarding the benefits of smoking cessation are important determinants of quitting. We anticipate that gain-framed texts will enhance expectations of the benefits of quitting smoking; so outcome expectancies will be evaluated as a mediator. We will administer 6 items from the Benefits subscale of the Perceived Risks and Benefits Questionnaire (health, well-being, self-esteem, finances, physical appeal, social approval). Participants will rate their perceptions of the benefits of quitting on a 7-point scale from 1 (*no chance*) to 7 (*certain to happen*). A similar brief measure of outcome expectancies has been shown to be a mediator of our framed message intervention with NY Quitline callers.

\*Fagerström Test for Nicotine Dependence (FTND) and Heaviness of Smoking Index (HSI): The HSI scale, which assesses 2 items from the FTND scale about amount smoked and time-to-first-cigarette, is a commonly used scale for the measurement of severity of dependence on nicotine. The HSI has been shown to predict both behavioral and biochemical indices of smoking. In line with findings from our previous research and from other groups, we plan to test both the FTND and HSI as moderators of treatment.

\*Self-efficacy: Tailored messages have been found to increase self-efficacy for smoking cessation; thus, we will examine self-efficacy as a mediator of treatment. We will measure self-efficacy using a single item. Participants will rate their confidence to quit smoking within the next month from 0 (*not at all confident*) to 10 (*completely confident*). A similar, single item self-efficacy measure has demonstrated predictive validity in smoking cessation studies, and in our previous research with the NY Quitline.

**Use of NRT and Other Pharmacotherapy:** We will determine the amount and frequency of NRT used (per product), and will determine use of products we provide (lozenge + patch) vs. additional purchase of products. We will ascertain the context in which the product is used (e.g., places with smoking restrictions vs. other) using prior methods. We will specifically ask if the NRT is used “not to quit, but to reduce the amount you smoke” or “not to quit or reduce smoking, but to get you through times when you cannot smoke.”

**\*Attitudes Towards NRT:** Based largely on prior work in this area, we have published on 1) positive, and 2) negative attitudes towards NRT, as well as 3) general knowledge of NRT.

**\*Motivation and Confidence to Quit:** We will separately assess motivation and confidence to quit smoking. We will do so using our modification of the Contemplation Ladder to measure readiness to quit in the next 1 and 6 months. Our ladders have adequate test-retest stability and predictive validity. This measure will of motivation will be used for stratification, as well as to assess motivation throughout treatment.

**Findings from screening:** Lung screening findings will be defined as pulmonary findings (nodule, cancer, emphysema, enlarged lymph nodes) and coronary findings (calcification).

**\*Lung Cancer Distress Questionnaire:** Higher baseline distress, as measured by the LCDQ has been associated short-term smoking cessation. We plan to use a single item from this questionnaire.

